### 17.3.1. CTCAE TOXICITY GRADES

Quantitative laboratory parameters with available CTCAE toxicity grades will be categorized as follows where

Author:	[name]	Version Number:	2.0
		Version Date:	23Nov2022
Template No.:	CS_TP_BS016 Revision 6	Reference:	CS_WI_BS005
Effective Date:	02Dec2019		

higher grades representing a more severe toxicity.

- Grade 1 (i.e., mild)
- Grade 2 (i.e., moderate)
- Grade 3 (i.e., severe)
- Grade 4 (i.e., life-threatening)
- Grade 5 (i.e., death)

Although not defined in the CTCAE toxicity grading system, version 4.03, non-missing laboratory parameter results not meeting any of the 5 grades defined in the CTCAE toxicity grading system will be categorized as 'No Event' for the purpose of the shift from baseline summaries.

### 17.3.2. LABORATORY NORMAL RANGES

Quantitative laboratory parameters will be compared with the relevant laboratory normal ranges in SI units and categorized as:

- Low: Below the lower limit of the laboratory normal range.
- Normal: Within the laboratory normal range (upper and lower limit included).
- High: Above the upper limit of the laboratory normal range.

## 17.4. VITAL SIGNS

The following vital sign parameters will be collected for this study as per the schedule of events (refer to protocol, Table 3):

- Systolic blood pressure (SBP) (mmHg)
- Diastolic blood pressure (DBP) (mmHg)
- Pulse rate (beats per minute [bpm])
- Oxygen saturation (%)
- Body temperature (°C)

Author:	[name]	Version Number:	2.0
Template No.:	CS_TP_BS016 Revision 6	Version Date:	23Nov2022
Effective Date:	02Dec2019	Reference:	CS_WI_BS005

- Weight (kg)

The following summaries will be provided by treatment group based on the SAF analysis population for each vital sign parameter:

- Observed and change from baseline by visit and timepoint
- Number and percentages of subjects with at least one markedly abnormal post-baseline observed value/change from baseline (refer to [Section 17.4.1](#))

All vital sign data will be listed. Vitals signs meeting one of the markedly abnormal criteria in Section 17.4.1 will be identified.

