## 5.7 Study Endpoints

Consistent with the study objectives, the primary endpoints will focus on the safety and tolerability of AVT001 treatment versus placebo.

The primary endpoints are:

- (a) The incidence of treatment-emergent adverse events (TEAEs).
- (b) Changes from baseline in clinical laboratory parameters.
- (c) The incidence and severity of local IV-site reactions.
- (d) Changes from baseline in vital signs and electrocardiograms.
- (e) Incidence of severe hypoglycemic events.

Secondary objectives focus on the CD8+ T-cell regulatory system and therapeutic outcomes associated with T1D. These pharmacodynamic effects of AVT001 will be assessed in an exploratory manner.

Secondary endpoints will include:

- (a) Assessment of the HLA-E-restricted CD8+ T cell regulatory activity (“potency assay”)
- (b) Changes from baseline in the area under the curve (AUC) of the stimulated C-peptide levels over the first 4 hours of a mixed meal tolerance test (MMTT)
- (c) Changes from baseline in HbA1c
- (d) Change from baseline in total daily insulin dose
- (e) Changes from baseline in autoantibody levels

The primary time point for analysis is Month 5, at which point the primary assessment of the study objectives is performed.

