#### **8.3.1 Study Days 1, 30 ± 7 days, and 60 ± 7 days**

On the first study day, a 4-hour Mixed Meal Tolerance Test (MMTT) will be performed as part of baseline evaluations. The meal test will be performed in the morning after an overnight fast, with no food or drink (with the exception of water). At the outset, a mixed meal, consisting of High Protein Boost will be administered. Blood samples for C-peptide and glucose will be collected at the following timepoints (in minutes, relative to administration of the mixed-meal): -10, 0, 15, 30, and then at 30 minute-intervals until the last time point of 240 minutes.

1-2 days prior to each study day, study personnel will contact the subject to confirm that they remain in generally good health and that there are no symptoms of acute illness.

Prior to dosing on Study Day 1, a review of eligibility should be performed and confirmed. If, prior to dosing, a randomized subject is not suitable (ineligible) for the trial, that subject will be considered a “randomization failure” and will be replaced.

The following procedures will be performed prior to study drug administration on each dosing day:

- Any changes to medical history including prior treatment, current medicines, and drug

- Focused physical exam including blood pressure, pulse, temperature and weight.
- Laboratory studies including:
  - CMP
  - CBC w diff
  - HbA1c
  - Urine MicroAlbumin panel
  - CrCl (calculation)
- 
- Measurement of auto-antibodies, including:
  - Insulin associated aAb (IAA)
  - Insulinoma associated protein 2 (IA-2, previously known as ICA-512)
  - Glutamic acid decarboxylase (GAD65)
  - Zinc transporter 8 (ZnT8).
- A urine pregnancy test will be collected for females of child-bearing potential.
- Any severe hypoglycemic events occurring since the prior study visit will be recorded. Note that non-severe events are not being collected in the database in this study, but will be monitored by the investigator, consistent with the site's standard of care.

Study drug will be administered during these visits. Laboratory data will be collected prior to initiation of the infusion of study drug.

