## 6.2. BASELINE

Unless otherwise specified, baseline is defined as the last non-missing measurement taken prior to the first injection of study drug (including unscheduled assessments). In the case where the last non-missing measurement and the date

Author:	[name]	Version Number:	2.0
		Version Date:	23Nov2022
Template No.:	CS_TP_BS016 Revision 6	Reference:	CS_WI_BS005
Effective Date:	02Dec2019		

and time of the first injection of study drug coincide, that measurement will be considered pre-baseline, but adverse events (AEs) and medications commencing on the date and time of the first injection of study drug will be considered post-baseline.

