## **6.5. COMMON CALCULATIONS**

Change from baseline will be calculated as:

- Change from baseline = Test value at baseline or post-baseline visit – Baseline value

Percent change from baseline will be calculated as:

- Percent change from baseline (%) = (Change from baseline at baseline or post-baseline visit / Baseline value) \* 100%

For select parameters where data is available, change and percent change will also be calculated from diagnosis.

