#### **17.4.1. VITAL SIGNS MARKEDLY ABNORMAL CRITERIA**

Markedly abnormal vital sign observed values and/or change from baseline will be identified in accordance with the following predefined markedly abnormal criteria:

Variable	Unit	Low	High
SBP	mmHg	≤ 90 mmHg AND change from baseline ≤ -20 mmHg	≥ 180 mmHg AND change from baseline ≥ 20 mmHg
DBP	mmHg	≤ 50 mmHg AND change from baseline ≤ -15 mmHg	≥ 105 mmHg AND change from baseline ≥ 15 mmHg
Pulse rate	bpm	≤ 50 bpm AND change from baseline ≤ -15 bpm	≥ 120 bpm AND change from baseline ≥ 15 bpm
Oxygen saturation	%	< 94 %	Not applicable
Body temperature	°C	Not applicable	≥ 38.3 °C AND change from baseline ≥ 1.1 °C
Weight	kg	Percent change from baseline ≤ -7.0 %	Percent change from baseline > 7.0 %

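### Vital-sign change at infusions 2 and 3 is measured only from the value before the first infusion; a same-day pre-infusion change should be added

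*Combined protocol and SAP*

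**What the plan says.** **Baseline.** SAP v2.0 section 6.2 gives one rule for all parameters: "Unless otherwise specified, baseline is defined as the last non-missing measurement taken prior to the first injection of study drug (including unscheduled assessments". Section 6.5 forms every change by subtracting that value from the "Test value at baseline or post-baseline visit".

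**Vital signs.** Section 17.4 asks for "Observed and change from baseline by visit and timepoint" and names no other reference. The markedly abnormal criteria in 17.4.1 for systolic and diastolic pressure and pulse, and the high criterion for temperature, each join an absolute limit to a change limit. Low systolic pressure, for example, is "≤ 90 mmHg AND change from baseline ≤ -20 mmHg". The oxygen saturation criterion has no change part, and weight uses percent change. SAP v1.0 has the same rules.

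**Endpoint.** Protocol Amendment 3, section 5.7, lists primary endpoint (d) as "Changes from baseline in vital signs and electrocardiograms". Section 9.7 plans descriptive change from Baseline to on-treatment.

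**Data collected.** Protocol 8.3.1 says "The following procedures will be performed prior to study drug administration on each dosing day", and the list includes "Focused physical exam including blood pressure, pulse, temperature and weight". Oxygen saturation is not named in it. Sections 5.3 and 8.3.1 then require vital-sign monitoring during each infusion and observation for at least 2 hours after it.

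**The concern.** The trial is a first-in-man study of an infused cell product, and safety is its primary objective. Protocol 5.3 has the site prepared at the bedside for cytokine release, anaphylactoid or infusion reactions, respiratory distress and arrhythmia. For reactions of that kind the informative quantity is how far a reading moved from just before the infusion to during or after it.

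The SAP expects several readings per visit: 17.4 tabulates vital signs by timepoint as well as visit, whereas 17.5 tabulates ECGs by visit only. Yet for two of the three infusions the planned change mixes the acute movement with whatever drift has occurred since Day 1. The pre-infusion readings of Days 30 and 60 serve only as further rows and never as a reference.

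**Working it through.** The plan states no figure on this point, so there is none to reproduce.

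**1. Age of the reference.** Protocol 7.1 places infusions 2 and 3 at Study Days 30 and 60, each ±7 days and at least 21 days apart. The first infusion is on Study Day 1.
- Infusion 2: Days 23 to 37, so 23 − 1 = 22 to 37 − 1 = 36 days after Day 1.
- Infusion 3: Days 53 to 67, so 53 − 1 = 52 to 67 − 1 = 66 days after Day 1.

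That is about 3 to 9 weeks. If the Day 1 pre-dose reading is missing, 6.2 falls back to an older one.

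**2. Individual flags under the full low-systolic rule (at most 90 mmHg and a change of −20 or lower).**

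| Day 1 | Before infusion 2 | After infusion 2 | Change from Day 1 | Same-day change |
|---|---|---|---|---|
| 105 | 125 | 90 | −15, not flagged | −35, would be flagged |
| 112 | 93 | 90 | −22, flagged | −3, would not be flagged |

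**3. Spread of the change.** Model a reading as subject mean + visit deviation (SD s_b) + within-visit error (SD s_w). Then

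SD(change from Day 1) = √(2s_b² + 2s_w²); SD(same-day change) = √(2s_w²).

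The documents give no SDs. For systolic pressure I assume s_b of 6 to 10 and s_w of 5 to 6 mmHg.

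| s_b, s_w | From Day 1 | Same-day | Between-visit share of variance |
|---|---|---|---|
| 6, 5 | √122 = 11.0 | √50 = 7.1 | 72/122 = 59% |
| 8, 5 | √178 = 13.3 | √50 = 7.1 | 128/178 = 72% |
| 10, 6 | √272 = 16.5 | √72 = 8.5 | 200/272 = 74% |

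**4. Flag rates under the full two-part rule.** Simulation of one post-infusion reading per subject, further assuming mean systolic pressure 118 and between-subject SD 12 mmHg. Each cell gives Day 1 reference / same-day reference.

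| s_b, s_w | No infusion effect | True 25 mmHg fall | Same-day flags missed by Day 1 rule (true fall) | Day 1 flags not flagged same-day (true fall) |
|---|---|---|---|---|
| 6, 5 | 0.4% / 0.03% | 33.6% / 34.7% | 17% | 14% |
| 8, 5 | 0.9% / 0.03% | 33.7% / 34.9% | 18% | 15% |
| 10, 6 | 2.0% / 0.14% | 34.1% / 34.3% | 19% | 18% |

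Overall detection is almost the same because the absolute limit is shared. The two references differ in which subjects they flag.

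**5. What one subject is worth.** With the planned 16 and 8 subjects, one misclassified subject moves a reported percentage by 1/16 = 6.25 or 1/8 = 12.5 points.

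**The case against.** **The SAP does what the protocol asks.** Endpoint (d) and section 9.7 both speak of change from baseline. A single pre-first-dose baseline also shows persistent shifts after earlier infusions, which a same-day reference would remove. This stands: the existing summary is legitimate and should stay. A reader might infer that the SAP uses a wrong baseline or departs from the protocol; the text supports neither.

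**The change limit alone exaggerates the effect.** Taken by itself, with the same SDs and no infusion effect, a change of −20 mmHg or lower occurs in 3.5 to 11% of readings from Day 1 against 0.2 to 0.9% same-day. A true 25 mmHg fall meets it in 62 to 67% against 72 to 76%. It is tempting to read these as false-flag rates and lost sensitivity. They are not, because 17.4.1 also requires the absolute limit; step 4 of the working gives the rates for the rule as written.

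**Acute reactions have other routes into the results.** Observed values are summarised by visit and timepoint, all vital signs are listed, subjects are observed at the bedside, and clinically significant findings can be reported as adverse events under endpoint (a). This limits the harm. But a table of group means by timepoint does not show within-subject change, and a listing is not a planned summary.

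**Some sources are not available.** Reading times are left to site standard of care and the MOP (Table 3, note 6), and layouts to the TFL shells. A same-day reference there cannot be excluded, but the SAP states none.

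**Conclusion.** The point holds as a gap in the planned safety description. At infusions 2 and 3, change in vital signs is taken from a value normally 22 to 36 and 52 to 66 days old, and no same-day pre-to-post change is planned although blood pressure, pulse and temperature are collected for it.

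The cost is noise and misclassified individual flags. On the assumed SDs, the SD of systolic change is 11.0 to 16.5 mmHg rather than 7.1 to 8.5. Flags without any infusion effect are about 0.4 to 2.0% rather than 0.03 to 0.14% per reading. A true 25 mmHg fall is flagged about 34% of the time under either reference, but 17 to 19% of the same-day flags are missed by the Day 1 rule. These sizes depend on the assumed SDs and mean, and per-subject rates depend on the number of readings, which the documents do not give. The age of the reference and the two worked cases depend on none of this.

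A reader might infer bias between AVT001 and placebo. The documents do not support that: both randomised arms follow the same infusion schedule and baseline rule, so drift is expected to be similar, and SAP 17 plans no safety comparisons. This is a worthwhile, cheap improvement, not the correction of an error.

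**What to change.** Keep change from the pre-first-dose baseline as it is. Add to SAP 17.4 and 17.4.1:

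- For readings during and after each infusion on Days 1, 30 and 60, summarise descriptively the change from the last pre-infusion value on the same day, by treatment group, visit and timepoint.
- Show the systolic, diastolic, pulse and temperature flags with their change part on both references, absolute limits unchanged.
- Leave weight out. The oxygen saturation flag needs no alteration; give its same-day change only where a pre-infusion reading was recorded.

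SAP v2.0 section 4.4 already foresees an amendment before the final lock, which can carry this. Section 4.2 records unblinding on 17 May 2022, so the new output should be labelled as a descriptive addition made after unblinding. The cost is one derivation and one table, with no new data. No p-value is affected, because safety data are not tested.

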#### **17.4.1. VITAL SIGNS MARKEDLY ABNORMAL CRITERIA**

Markedly abnormal vital sign observed values and/or change from baseline will be identified in accordance with the following predefined markedly abnormal criteria:

Variable	Unit	Low	High
SBP	mmHg	≤ 90 mmHg AND change from baseline ≤ -20 mmHg	≥ 180 mmHg AND change from baseline ≥ 20 mmHg
DBP	mmHg	≤ 50 mmHg AND change from baseline ≤ -15 mmHg	≥ 105 mmHg AND change from baseline ≥ 15 mmHg
Pulse rate	bpm	≤ 50 bpm AND change from baseline ≤ -15 bpm	≥ 120 bpm AND change from baseline ≥ 15 bpm
Oxygen saturation	%	< 94 %	Not applicable
Body temperature	°C	Not applicable	≥ 38.3 °C AND change from baseline ≥ 1.1 °C
Weight	kg	Percent change from baseline ≤ -7.0 %	Percent change from baseline > 7.0 %

## 17.5. ECG EVALUATIONS

The following electrocardiogram (ECG) parameters will be measured for this study as per the schedule of events (refer to protocol, Table 3):

- PR interval (msec)
- RR interval (msec)
- QRS interval (msec)
- QT (uncorrected) interval (msec)
- Overall ECG evaluation (Investigator's judgment)
  - Normal
  - Abnormal, not clinically significant (NCS)
  - Abnormal, clinically significant (CS)

The following summaries will be provided by treatment group based on the SAF analysis population for each ECG parameter:

- Observed and change from baseline by visit (for quantitative parameters)
- Number and percentages of subjects with at least one markedly abnormal post-baseline observed value/change from baseline (for quantitative parameters; refer to [Section 17.5.11](#))
- Shift from baseline in overall ECG interpretation to the worst post-baseline assessment

All ECG data will be listed. ECG results meeting one of the markedly abnormal criteria in Section 17.5.1 will be identified.

### 17.5.1. ECG MARKEDLY ABNORMAL CRITERIA

Markedly abnormal quantitative ECG parameters will be identified in accordance with the following predefined markedly abnormal criteria:

- Observed values for QT (uncorrected) interval will be classified as:

Author:	[name]	Version Number:	2.0
Template No.:	CS_TP_BS016 Revision 6	Version Date:	23Nov2022
Effective Date:	02Dec2019	Reference:	CS_WI_BS005

- > 450 msec
  - > 480 msec
  - > 500 msec
- Change from baseline for QT (uncorrected) interval will be classified as:
  - >30 msec increase from baseline
  - >60 msec increase from baseline

It is to be noted that the previous categories are not mutually exclusive, but cumulative. For example, if a subject worst post-baseline QT post-baseline observed value is 490 mmHg, then this subject will be reported once under QT > 450 msec and once under QT > 480 msec.

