#### **8.5 ECGs**

All scheduled ECGs will be performed after the subject has rested supine for approximately 5 minutes. ECGs will be collected during Screening and Day 90 ± 7 days

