## 2. STUDY OBJECTIVES AND ENDPOINTS

### 2.1. PRIMARY OBJECTIVE AND ENDPOINTS

Objectives	Endpoints
To determine the safety and tolerability profile of three doses of AVT001 (as compared to placebo) in T1D subjects within-vitro -reversible defects in the CD8+ T cell regulatory system.	Incidence of treatment-emergent adverse events (TEAEs).  Clinically significant changes from baseline in clinical laboratory parameters.  Incidence and severity of local IV-site reactions.  Changes from baseline in vital signs and electrocardiograms.  Incidence of severe hypoglycaemic events.

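### The only numeric ECG abnormality flags are set on uncorrected QT although RR is recorded, so they depend on heart rate; a QTcF version should be added beside them

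*Combined protocol and SAP*

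**What the plan says.** SAP v2.0, Section 2.1, lists "Changes from baseline in vital signs and electrocardiograms" among the primary endpoints. Section 17.5 names the quantitative parameters: PR, RR, QRS and QT, the last expressly uncorrected. It plans three summaries by treatment group in the safety population:

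- descriptive statistics by visit;
- counts of subjects with at least one markedly abnormal value or change;
- "Shift from baseline in overall ECG interpretation to the worst post-baseline assessment", which rests on the investigator's judgement.

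All ECG data are also listed.

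Section 17.5.1 supplies the criteria for the second summary. "Observed values for QT (uncorrected) interval will be classified as" above 450, above 480 and above 500 msec. "Change from baseline for QT (uncorrected) interval will be classified as" an increase of more than 30 or more than 60 msec. PR, RR and QRS have no such criteria. SAP v1.0 has the same text. Neither the protocol nor either SAP derives a corrected QT.

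On timing, Protocol Amendment 3, Section 8.5, states that "ECGs will be collected during Screening and Day 90", after about five minutes of supine rest. Table 3 of the protocol schedules no other ECG.

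**The concern.** QT shortens as the heart speeds up and lengthens as it slows. A fixed limit on raw QT is therefore strict at slow rates and lenient at fast ones, and a change in raw QT mixes any change in repolarisation with any change in pulse. These flags are the whole numeric abnormality table for the ECG part of a primary endpoint.

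Each subject has one scheduled ECG before treatment and one after. The first can be up to 90 days before dosing and the second is at Day 90, so the pair can be about 90 + 90 = 180 days apart. Differences in rate between the two recordings are not averaged out. In the planned arms of 16 and 8, one misplaced flag moves a reported percentage by 1/16 = 6.25 or 1/8 = 12.5 points.

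**Working it through.** The plan attaches no power, alpha or expected count to the ECG endpoint, so there is no figure of its own to reproduce. The check asks what the stated limits mean on a rate-corrected scale.

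**Inputs from the documents:** the limits of 450, 480 and 500 msec and of +30 and +60 msec (SAP 17.5.1), and RR recorded in msec (SAP 17.5).

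**Assumptions, not in the documents:** heart rates from 50 to 100 bpm, the QTc values used below, and two standard corrections.

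- Fridericia: QTcF = QT/(RR/1000)^(1/3)
- Bazett: QTcB = QT/(RR/1000)^(1/2)
- RR = 60000/heart rate

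**Absolute limits.** The first two result columns give the corrected value when raw QT is exactly 450 ms, which is not flagged. The last gives the raw QT produced by a true QTcF of 500 ms.

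| bpm | RR (ms) | QTcF at QT 450 | QTcB at QT 450 | Raw QT at QTcF 500 |
|---|---|---|---|---|
| 50 | 1200 | 423 | 411 | 531 |
| 60 | 1000 | 450 | 450 | 500 |
| 80 | 750 | 495 | 520 | 454 |
| 90 | 667 | 515 | 551 | 437 |
| 100 | 600 | 534 | 581 | 422 |

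Example: at 80 bpm, 450/(0.75)^(1/3) = 495.

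- *Missed.* A QTcF of 500 ms reaches only the lowest category at 80 bpm (454 ms) and no category at 90 or 100 bpm. A QTc above 500 ms can escape every absolute flag from about 60 × (500/450)^3 = 82 bpm with Fridericia, or 60 × (500/450)^2 = 74 bpm with Bazett.
- *False.* A QTcF of 430 ms at 50 bpm gives raw QT 430 × (1.2)^(1/3) = 457 ms, flagged above 450.

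**Change limits.**

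- *False.* Hold QTcF at 410 ms and let the rate fall from 80 to 60 bpm. Raw QT goes from 410 × (0.75)^(1/3) = 372.5 to 410.0 ms, an increase of 37.5 ms, flagged above 30. With QTc constant at 400 ms the same fall gives +36.6 ms (Fridericia) or +53.6 ms (Bazett).
- *Borderline.* A fall from 75 to 60 bpm gives +28.7 ms at QTcF 400 and +30.1 ms at QTcF 420. Under Fridericia, a drop of about 15 bpm in this range is therefore roughly where false flags begin.
- *Masked.* Let QTcF rise from 410 to 470 ms while the rate goes from 60 to 90 bpm. Raw QT goes from 410.0 to 470 × (0.667)^(1/3) = 410.6 ms, an increase of 0.6 ms, so a true rise of 60 ms raises no flag.

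Both directions of error appear under both corrections, so the conclusion does not depend on the formula. The fall from 80 to 60 bpm would not itself be flagged: SAP 17.4.1 calls pulse markedly abnormal only at 50 bpm or below, or 120 bpm or above, together with a change of at least 15 bpm.

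**The case against.** The strongest reply is that little hangs on these flags. They are one of three ECG summaries. The investigator's rating is made separately, QT and RR are both listed, and the protocol (11.1.2) makes an abnormal diagnostic result an adverse event if the investigator considers it clinically significant. SAP Section 17 plans no between-group comparison of safety data, and the stopping rules (protocol 5.6.1) use toxicity grades, not ECG categories. The SAP labels the variable as uncorrected. ECGs are taken supine after rest, the documents give no heart-rate distribution, and the listed risks name no repolarisation concern. All of this stands and limits the weight of the point. It does not repair a numeric table whose limits change meaning with pulse. Because safety is descriptive, that table is itself a reported result.

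A reader might infer three stronger things that the documents do not support:

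- *That an unflagged subject is reported as normal.* The word normal comes only from the investigator's rating, which 17.5.1 does not drive.
- *That one wrong flag settles a subject's ECG outcome, or that true prolongation goes unseen.* The other summaries and the listings remain; what can be missed is missed by the numeric flags.
- *That the raw-QT table should be replaced.* Under SAP v2.0, Section 4.2, the Month 5 analysis was unblinded on 17 May 2022 and delivered on 10 June 2022, and v1.0 had the same ECG rule. Replacing a prespecified safety table after unblinding would break comparability with that output.

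**Conclusion.** The point holds for the numeric flags. As written, 17.5.1 can miss prolongation at faster rates and raise false flags at slower rates or after slowing. Between 50 and 100 bpm, the single raw limit of 450 ms spans QTcF values from about 423 to 534 ms. A fall of 20 bpm from 80 bpm is enough for a false increase above 30 msec.

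These sizes rest on assumed heart rates and QTc values and on the Fridericia formula. Bazett gives a wider spread. How many of the roughly 24 subjects would change category is unknown and could be none. Nothing here shows that the delivered Month 5 safety conclusion is wrong. Severity is minor to moderate: a weakness in one descriptive summary of a primary safety endpoint, correctable from data already recorded.

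**What to change.** In SAP 17.5, add the derived variable QTcF = QT/(RR/1000)^(1/3), computed from the QT and RR of the same ECG. In 17.5.1, apply the existing absolute categories (above 450, 480 and 500 ms) and change categories (above 30 and 60 ms) to QTcF in the supplemental Day 360 analysis and the final analysis. Record it in the section on changes to the planned analyses as added after the Month 5 unblinding. Keep the raw-QT table beside it so that the output can be compared with what was delivered. Section 4.4 already provides for a SAP amendment before the final lock.

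The cost is one derived variable and one extra table, with no new data or procedure. No ECG is scheduled after Day 90, so apart from any unscheduled tracings the new table will describe the same ECGs as the Month 5 output. The drawback is that it is added with the treatment codes known. A fixed formula and unchanged limits leave little room for choice, but the label is still needed. In the same edit, the worked example in 17.5.1, which gives a QT value in mmHg, should read msec.
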